8.1.9. Clinical status using 8-category ordinal scale of patient health status

An 8-category ordinal scale of patient health status ranges will be used to collect subject clinical status where

- 0 = no clinical or virological evidence of infection;
- 1 = no limitation of activities;
- 2 = limitation of activities;
- 3 = hospitalized, no oxygen therapy;
- 4 = oxygen by mask or nasal prongs;
- 5 = non-invasive ventilation or high-flow oxygen;
- 6 = intubation and mechanical ventilation;
- 7 = ventilation + additional organ support – pressors, rapid response team (RRT), extracorporeal membrane oxygenation (ECMO);
- 8 = death.

See [Section 14.2](#) for form.

8.1.10. IRT Registration, Randomization and Study Discontinuation or Completion.

Subjects will be registered in IRT after signing informed consent and will be randomized using the IRT on Day 1 to either Treatment Arm 1 (STI-5656 plus SOC) or Treatment Arm 2 (placebo plus SOC) using central integrated response technology (IRT). Subject study discontinuation or study completion should also be registered in the IRT.

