3.2.2. Secondary Endpoints

- Types, frequencies, and severities of AEs and the relationships of AEs to IP; includes serious adverse events SAEs
- Proportion of subjects alive and free of respiratory failure at Day 60
- Change in clinical status (on a 0-8-point ordinal scale²) of subject at Day 7, Day 14, and Day 28
- Proportion of subjects alive and discharged from ICU at Days 14 and 28

² 8-category ordinal scale of patient health status ranges: 0=no clinical or virological evidence of infection; 1=no limitation of activities; 2=limitation of activities; 3=hospitalized, no oxygen therapy; 4=oxygen by mask or nasal prongs; 5=non-invasive ventilation or high-flow oxygen; 6=intubation and mechanical ventilation; 7=ventilation + additional organ support – pressors, rapid response team (RRT), extracorporeal membrane oxygenation (ECMO); 8=death.

- Time from randomization to first occurrence of respiratory failure or death on study due to any cause up to Day 28
- Percent change from baseline in CRP at Days 3, 5, 7, 10, 14, 28
- Relative change from baseline in oxygenation index (PaO₂/FiO₂) up to Day 5
- All-cause mortality at Day 60 and Day 90
- Number of days alive and free of respiratory failure at Day 28
- Number of days with respiratory failure up to Day 28
- Number of days hospitalized up to Day 28
- Number of days in ICU (length of stay) up to Day 90
- Number of days alive outside of hospital up to Day 28
- Number of days alive outside of hospital up to Day 90
- To assess the pharmacokinetic profile in the study population

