6.3. Stopping Rule Triggers

Study drug dose should be paused per the guidelines in [Table 2](#) (using the Common Terminology Criteria for Adverse Events, Version 5.0 [CTCAE] for severity grading).

Table 2: Stopping Rule Triggers

If any of the following possibly related AEs occur:	At the first occurrence of any of the stopping rule triggers, discontinue Study Drug for the affected subject and pause further enrollment until DMC deliberations have been completed and a DMC decision that enrollment may be restarted has been rendered.

 • \geq Grade 3 (G3) non-hematologic toxicities • \geq G3 alanine aminotransferase (ALT) elevation OR \geq any ALT and total bilirubin elevation in combination which meet Hy's Law criteria [i.e., any \geq G3 hepatic impairment] • G3 thrombocytopenia with bleeding • G4 thrombocytopenia • G4 neutropenia • G3 neutropenia or thrombocytopenia in > 3 subjects • \geq G3 renal impairment including acute kidney injury requiring hemodialysis • Any SUSAR (suspected unexpected serious adverse reaction) 	

A DMC teleconference will be arranged within 5 business days of the stopping rule trigger. This should provide sufficient time for the CRO to prepare a blinded summary of the AE and the independent statistician to arrange to be unblinded to assist the DMC in its deliberations.

Additionally, the DMC will be provided with tabular safety summaries at 25%, 50% and 75% enrollment for ongoing surveillance.

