9.4.5. Secondary Endpoints (Efficacy)

The proportion of subjects alive and discharged from the ICU at Day 14 and Day 28 and the proportion alive and free of respiratory failure at Day 60 and will be presented and analyzed as described for the primary efficacy endpoint. Subjects who discontinue from the study prior to each study day will be considered treatment failures.

Clinical Status will be assessed using a generalized linear mixed model, assuming a multinomial distribution. The model will include the Day 1 value as a covariate with fixed effects of group,

study day and group-by-study day interaction and subject as a random effect. If the group-by-study day interaction is found to be statistically significant then comparisons between groups at Day 7, Day 14 and Day 28 will be obtained from this model. Additionally, stacked bar charts will be presented for the proportion of subjects in each category by group and study day.

For the time from randomization to first occurrence of respiratory failure or death on study due to any cause, the Kaplan-Meier method will be applied. Subjects will be censored at the time of last follow-up. For each group, the 25th percentile, median and 75th percentile will be presented, if possible. Possible differences between groups will be assessed by the log-rank test.

The total number of deaths per group will be presented for All-cause mortality at Day 90.

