14. APPENDICES

14.1. List of Abbreviations and Definitions of Terms

The following abbreviations and specialist terms are used in this study protocol.

Table 3: Abbreviations

Abbreviation	Explanation
ADL	Activities of daily living
AE	Adverse Events
ALC	Absolute lymphocyte count
ALT	Alanine aminotransferase
AST	aspartate aminotransferase
B-hCG	Beta human chorionic gonadotropin
CONSORT	Consolidated Standards of Reporting Trials
COVID-19	Coronavirus 2019
CRP	C-reactive protein
CTCAE	Common Terminology Criteria for Adverse Events, Version 5.0
DMC	Data monitoring committee
EC	Ethics Committee
ECG	Electrocardiogram
ECMO	Extracorporeal membrane oxygenation
e-CRF	Electronic case report form
ET	Early Termination
F	Fahrenheit
FA	Full analysis
FDA	Food and Drug Administration
FCBP	Female of child-bearing potential
FiO ₂	Fraction of inspired oxygen
FSH	Follicle stimulating hormone
G	Grade
ICF	Informed consent form
ICH	International Council for Harmonisation
ICU	Intensive Care Unit
IRT	Interactive Response Technology

Abbreviation	Explanation
JAK	Janus kinase
L/min	Liters per minute
MedDRA	Medical Dictionary for Regulatory Activities
miU	Milli international units
mL	Milliliters
PaO ₂	Partial pressure of oxygen in arterial blood
PI3K	Phosphoinositide 3 kinase
p.o.	By mouth
PP	Per protocol
PT	Preferred term
QD	Once daily
RBC	Red blood cells
Rbc/hpf	Red blood cells per high power field
RRT	Rapid response team
RT-PCR	Reverse transcriptase polymerase chain reaction
SAE	Serious adverse event
SARS-CoV-2	severe acute respiratory syndrome coronavirus 2
SAS	Statistical Analysis System
SOA	Schedule of Assessments
SOC	Standard of Care
SOC	System organ class
SOP	Standard operating procedures
TEAE	Treatment-emergent adverse events
ULN	upper limit of normal
VEGF	Vascular endothelial growth factor
WBC	White blood cells
WHO	World Health Organization

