14.2. Ordinal Scale for Clinical Improvement

Ordinal Scale for Clinical Improvement

Patient State	Descriptor	Score
Uninfected	No clinical or virological evidence of infection	0
Ambulatory	No limitation of activities	1
	Limitation of activities	2
Hospitalized Mild disease	Hospitalized, no oxygen therapy	3
	Oxygen by mask or nasal prongs	4
Hospitalized Severe Disease	Non-invasive ventilation or high-flow oxygen	5
	Intubation and mechanical ventilation	6
	Ventilation + additional organ support – pressors, RRT, ECMO	7
Dead	Death	8

Source: https://www.who.int/blueprint/priority-diseases/key-action/COVID-19_Treatment_Trial_Design_Master_Protocol_synopsis_Final_18022020.pdf

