Chemistry: performed locally. 14-analyte complete metabolic panel (CMP): Albumin, alkaline phosphatase (ALP), alanine aminotransferase (ALT), aspartate aminotransferase (AST), bicarbonate, total bilirubin (TBIL), blood urea nitrogen (BUN), calcium, chloride, creatinine, glucose, potassium, sodium, total protein, D-dimer, fibrinogen.

 Cytokines include TNF $\alpha$ , IFN $\gamma$ , IL-6, IL-1 $\beta$ , IL-7, IL-8, IL-10, IL-12, IL-17, IL-18, IP 10, VEGF-A

 Record FiO2 (and PaO2) at the time of arterial blood gas sampling. If PaO2 is not available, use SpO2. Other respiratory status data to collect includes oxygen supplementation status: mechanical ventilation, face mask, nasal cannula or room air. Radiographic findings will also be collected.

 AEs will be collected from the time of informed consent to Day 60. Any ongoing AEs at Day 28 will be followed until resolution or stabilization.

 An 8-category ordinal scale of patient health status ranges: 0=no clinical or virological evidence of infection; 1=no limitation of activities; 2=limitation of activities; 3=hospitalized, no oxygen therapy; 4=oxygen by mask or nasal prongs; 5=non-invasive ventilation or high-flow oxygen; 6=intubation and mechanical ventilation; 7=ventilation + additional organ support – pressors, rapid response team (RRT), extracorporeal membrane oxygenation (ECMO); 8=death. See Section 18.2 for form.

 STI-5656 or placebo administration up to Day 14 or hospital discharge, whichever is sooner for subjects in Treatment Arm 1. Study drug capsules should be taken orally with 200-250 mL of water following at least 2 hours of fasting.

 Samples will be collected from the first 20 subjects enrolled. Sampling timepoints are as follows: Day 1 (predose) and at 0.5, 1, 2, 4, 8, 12, postdose on dosing days 1 and 8.

CONFIDENTIAL

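### Ordinal score 7 lists a rapid response team as organ support, where RRT fits only renal replacement therapy, so the boundary between scores 6 and 7 is wrong or inconsistent between sites

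*Protocol*

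**What the plan says.** Protocol 8.1.9 sets out the scale used to score clinical status. The two ventilated levels are "6 = intubation and mechanical ventilation" and, one step worse, "ventilation + additional organ support – pressors, rapid response team (RRT), extracorporeal membrane oxygenation (ECMO". The list after the dash is not marked as a set of examples, and no level of the scale mentions dialysis or any other renal support.

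The same expansion of RRT stands in the synopsis footnote, the schedule's abbreviation key and footnote 14, and the footnote to Protocol 3.2.2. The abbreviation list in Protocol 14.1 gives it as "Rapid response team" and offers no other meaning. The SAP repeats it in its own abbreviation list, in the Appendix 1 key, and in Appendix 1 footnote 14: "7=ventilation + additional organ support – pressors, rapid response team (RRT), extracorporeal membrane oxygenation (ECMO".

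The scoring form in Protocol 14.2 leaves the abbreviation unexpanded: "Ventilation + additional organ support – pressors, RRT, ECMO".

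The scale feeds the secondary endpoint of change in clinical status "of subject at Day 7, Day 14, and Day 28" (Protocol 3.2.2). On analysis, Protocol 9.4.5 states: "Clinical Status will be assessed using a generalized linear mixed model, assuming a multinomial distribution". SAP 9.2.2 gives only descriptive summaries and stacked bar charts, and fills missing days with the last known score. SAP 1.0 says that the SAP overrides the protocol's analysis description.

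**The concern.** Score 7 is meant to separate ventilated patients who need a further organ supported from those who need ventilation alone. Pressors and ECMO are such supports. A rapid response team is a group of staff who attend a deteriorating patient, so it does not belong under that heading. The natural reading of RRT in that position is renal replacement therapy. That reading is nowhere in either document, and a rater who looks the abbreviation up is sent to the wrong meaning.

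Dialysis is foreseeable in this trial. The stopping rules in Protocol 6.3 name "renal impairment including acute kidney injury requiring hemodialysis". Exclusion criterion 11 keeps out subjects with eGFR below 60 ml/min, so dialysis during the study would usually mark new deterioration, which a severity scale ought to register.

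At stake is the meaning of the two categories just below death. If response-team attendance counts, score 7 depends partly on how each hospital uses such teams. If sites resolve the wording differently, the same patient gets different scores at different sites.

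**Working it through.** No published figure is available to reproduce, so the check is textual.

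**Step 1: is this a single slip?** No. RRT is expanded as a response team in nine places: the synopsis footnote, the protocol schedule key, protocol schedule footnote 14, 3.2.2, 8.1.9, 14.1, the SAP abbreviation list, the SAP Appendix 1 key and SAP Appendix 1 footnote 14. Only the 14.2 form leaves it unexpanded. SAP 1.0 says it is based on protocol V5.0, whereas the protocol reviewed is Version 4.0. The wording therefore persists in a document written against the later version.

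**Step 2: apply the definition to two subjects.** Both are intubated and ventilated, and neither receives pressors or ECMO. Subject A is on dialysis. Subject B has been attended by a response team and is not on dialysis.

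| Reading of score 7 | Subject A (dialysis) | Subject B (team call) |
|---|---|---|
| Literal, closed list, RRT as expanded | no listed item met: 6 | listed item met: 7 |
| By the heading (is another organ being supported?) | yes: 7 | no: 6 |
| 14.2 form, RRT taken as renal replacement therapy | listed item met: 7 | no listed item met: 6 |

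The literal reading reverses the order of the two subjects compared with the other two readings. Each score moves by one category.

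**Step 3: what depends on the 6/7 boundary?**
- Primary endpoint (Protocol 3.2.1, SAP 9.1): it has its own definition of respiratory failure, which includes intubation with mechanical ventilation. Scores 6 and 7 are both ventilated states, so both subjects are failures whichever score they get. The other respiratory-failure endpoints follow the same definition.
- Clinical status at Days 7, 14 and 28: the counts in categories 6 and 7 change. Under SAP 9.2.2 a last recorded 6 or 7 is repeated on later days with no score, so one wrong score can appear at more than one reporting day.
- If the multinomial model of Protocol 9.4.5 were run, the same scores would enter it. SAP 9.2.2 contains no between-group test of this endpoint.

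**Step 4: can the number affected be computed?** No. The documents give no rate of ventilation, dialysis or response-team calls. The sample size assumptions (Protocol 9.2: 95.7% and 70% success, 40 per arm) give only a loose ceiling for Day 28. Expected failures are 40 × (1 − 0.957) + 40 × (1 − 0.70) = 1.72 + 12 = 13.72. That total also includes deaths (score 8), non-invasive ventilation or high-flow oxygen (score 5) and dropouts. Ventilated survivors at Day 28 would be some unknown part of about 14, and those whose score turns on this wording a smaller part still. No comparable figure exists for Days 7 or 14.

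**The case against.** The strongest objection is that the literal result may not occur in practice. Dialysis is organ support, the heading of score 7 says so in general terms, and the form that 8.1.9 points to prints only the abbreviation. An experienced clinician may well read it as renal replacement therapy and score 7. This stands in part: one cannot say that every ventilated, dialysed subject will be scored 6. But the definition then works only for raters who ignore the expansion that the documents print. Others will follow it, and the result is inconsistent scoring.

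A reader might also infer that the wording hides renal failure. The documents do not support that. Creatinine and BUN are in the inpatient chemistry, kidney injury is recorded as an adverse event and appears in the stopping rules when possibly related to study drug, and SAP 10.2 provides shift tables. The loss is confined to the ordinal scale. Even when corrected, the scale would not register dialysis in a subject who is not ventilated.

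It is fair, too, that the analytic effect is small: adjacent categories, one secondary endpoint, descriptive reporting. Finally, the form attributes the scale to an external source that was not available here. The intended meaning of RRT is therefore inferred from its position in the list.

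**Conclusion.** The scoring definition is wrong as written. It lists something that is not organ support as organ support, and it omits the one item that the abbreviation fits. The consequence is a 6/7 boundary that is wrong under the literal reading, or inconsistent between sites under mixed readings. The size is one category per affected subject, in either direction, limited to categories 6 and 7 of clinical status at Days 7, 14 and 28 and possibly repeated where the last score is carried forward. The primary endpoint and the monitoring of renal safety do not change.

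Two conclusions rest on reading choices: dialysis scored 6 requires the list to be read as closed, and the intended meaning of RRT is taken from context.

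A reader might be tempted to count the affected subjects. If 10 to 20% of 80 were ventilated at some time and 15 to 30% of those dialysed without pressors or ECMO, the count would run from 80 × 0.10 × 0.15 = 1.2 to 80 × 0.20 × 0.30 = 4.8. None of those rates is in the documents, and they count subjects ventilated at any time, not on the endpoint days. The range should not be used as an estimate.

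The point merits a correction before unblinding, but it does not threaten the trial's main conclusion.

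**What to change.** Replace the expansion with renal replacement therapy in every place where RRT is spelled out: the synopsis footnote; the protocol schedule's abbreviation key and footnote 14; Protocol 3.2.2, 8.1.9 and 14.1; the SAP abbreviation list; and the SAP Appendix 1 key and footnote 14. Spell the term out on the 14.2 form. Correcting only some of these would leave the documents contradicting themselves. Check protocol V5.0, on which the SAP is based, for the same wording.

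Send sites a short notice of how renal support is scored in ventilated subjects. Before unblinding, check every score of 6 or 7 already entered against source records for dialysis, pressors and ECMO, and correct it where needed.

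The cost is a wording change in nine places plus the form, one notice, and a review of the ventilated subjects' scores. The review needs hospital records, because dialysis and ECMO are not named among the respiratory status data in Protocol 8.1.8. Monitors already have electronic access to source records (Protocol 11.1). No assessment, visit or treatment changes.

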8.1.11. Adverse Events

Adverse events will be collected from the time of signing the ICF through Day 60.

8.1.12. Follow-up contact

The subject will be seen on Day 28 to collect laboratory samples, report on any additional AEs and on the status of unresolved AEs. The subject will also be contacted at Day 60 and 90 to document survival (or collect date of death from family or subject's physician). In addition, any experimental medication, duration of any additional hospital or ICU admissions after the first "post-randomization" discharge will also be collected.

8.2. Procedures by Study Day

8.2.1. Screening

- Informed Consent
- Registration of screening in IRT
- RT-PCR assay for SARS-CoV-2 (if needed, see details in [Section 8.1.2](#))
- Collection of Demographics, Medical History, Prior and Concomitant Medications
- Vital Signs
- Physical Exam
- 12-lead ECG
- Clinical laboratory tests per [Section 8.1.7](#)
- Respiratory Status
- Clinical status using 8-category ordinal scale of patient health status
- Assess eligibility

8.2.2. Study Day 1

- Vital Signs
- Clinical laboratory tests per [Section 8.1.7](#)
- Respiratory Status
- Collect adverse events since screening
- Collect con meds
- Clinical status using 8-category ordinal scale of patient health status
- Randomization in IRT
- Dispense STI-5656 or placebo capsules to subjects which should be taken orally with 200-250 mL of water following at least 2 hours of fasting.
- 12-lead ECG to be performed between 2 and 4 hours post study drug dosing

8.2.3. Daily until Hospital Discharge

- Vital Signs
- Clinical laboratory tests per [Section 8.1.7](#). Note that the urine pregnancy test is performed only at Screening, prior to randomization on Day 1 and at hospital discharge.
- Respiratory Status
- Collect adverse events

- Collect con meds
- Clinical status using 8-category ordinal scale of patient health status
- Dispense Study Drug to subjects which should be taken orally with 200-250 mL of water following at least 2 hours of fasting.

8.2.4. Hospital Discharge or Early Termination from Study

- Physical Exam
- Vital Signs
- Clinical laboratory tests per [Section 8.1.7](#)
- Respiratory Status
- Collect adverse events
- Collect con meds
- Clinical status using 8-category ordinal scale of patient health status
- If early termination, register in IRT

8.2.5. Outpatient Follow-up Day 28

- Collect AEs, and update status on previously unresolved AE status
- Clinical laboratory tests per [Section 8.1.7](#)
- Collect survival, experimental medications since hospital discharge, any new hospitalizations/ ICU stays

8.2.6. Telephone Follow-up Day 60

- Update status on previously unresolved AEs
- Collect survival, experimental medications since hospital discharge, any new hospitalizations/ ICU stays

8.2.7. Telephone Follow-up Day 90

- Update status on previously unresolved AEs
- Collect survival, experimental medications since hospital discharge, any new hospitalizations/ ICU stays

8.3. Blood Volumes collected

Blood for hematology, coagulation and chemistry should be standard of care along with the addition of D-dimer and fibrinogen to the chemistry assessments. Blood collected for measuring CRP, serum ferritin and cytokines (IL-6, TNF- α , IFN γ , IL1 β , IL-7, IL-10, IL-12, IL-17, IL-18 is approximately 6.5 mL per time point. Time points are Day 1 (baseline), Day 3, 7, 10, 14 and 28 (or at hospital discharge). The total blood volume collected for these measurements is approximately 60 mL per subject.

9. STATISTICS

9.1. Statistical Considerations

All tests of significance will be assessed at alpha level=0.05, 2-sided. All analyses and data presentations will be generated using SAS version 9.4, or higher (Cary, NC).

Subjects who are randomized to the study and discontinue before the end of the study will not be replaced. Missing values will not be imputed. For success/failure endpoints, subjects who discontinue prior to the specified time point will be included in the analysis as treatment failures and censored at the last day of follow-up for the time-to-event analysis. For all other endpoints, the mixed effect model repeat measurement (MMRM) analysis will be employed. The MMRM analysis only includes the available data. It has been demonstrated that the MMRM approach leads to estimators with comparatively small bias, and controls Type I error rates at a nominal level in the presence of missing completely at random (MCAR) or missing at random (MAR) and some possibility of missing not at random (MNAR) data (see <https://pubmed.ncbi.nlm.nih.gov/19212876/>).

9.2. Sample Size Estimation

An evaluable sample size of 40 subjects per group will provide 80% power (alpha=0.05, 2-sided) to detect a difference between groups in the number of subjects alive and free of respiratory failure at Day 28. This assumes that 95.7% of subjects who received STI-5656 plus SOC and 70% of subjects who received placebo plus SOC only will be alive and free of respiratory failure at Day 28. This represents a treatment effect difference of approximately 26%.

